26.4. Declaration of Helsinki

Recommendations Guiding Medical Physicians in Biomedical Research Involving Human Volunteers

Adopted by the 18th World Medical Assembly, Helsinki, Finland, June 1964
amended by the 29th World Medical Assembly, Tokyo, Japan, October 1975
and the 35th World Medical Assembly, Venice, Italy, October 1983
and revised 41st World Medical Assembly Hong Kong, 1989
and by the 48th World Medical Assembly, South Africa, October 1996

Introduction

It is the mission of the physician to safeguard the health of the people. His or her knowledge and conscience are dedicated to the fulfilment of this mission.

The Declaration of Geneva of the World Medical Association binds the physician with the words, "The health of my patient will be my first consideration", and the International Code of Medical Ethics declares that, "A physician shall act only in the patient's interest when providing medical care which might have the effect of weakening the physical and mental condition of the patient".

The purpose of biomedical research involving human volunteers must be to improve diagnostic, therapeutic and prophylactic procedures and the understanding of the aetiology and pathogenesis of disease.

In current medical practice most diagnostic, therapeutic or prophylactic procedures involve hazards. This applies especially to biomedical research.

Medical progress is based on research which ultimately must rest in part on experimentation involving human volunteers.

In the field of biomedical research a fundamental distinction must be recognised between medical research in which the aim is essentially diagnostic or therapeutic for a patient, and medical research, the essential object of which is purely scientific and without implying direct diagnostic or therapeutic value to the person volunteered to the research.

Special caution must be exercised in the conduct of research which may affect the environment, and the welfare of animals used for research must be respected.

Because it is essential that the results of laboratory experiments be applied to human beings to further scientific knowledge and to help suffering humanity, the World Medical Association has prepared the following recommendations as a guide to every physician in biomedical research involving human volunteers. They should be kept under review in the future.

It must be stressed that the standards as drafted are only a guide to physicians all over the world. Physicians are not relieved from criminal, civil and ethical responsibilities under the laws of their own countries.

I. Basic Principles

Biomedical research involving human volunteers must conform to generally accepted scientific principles and should be based on adequately performed laboratory and animal experimentation and on a thorough knowledge of the scientific literature.

The design and performance of each experimental procedure involving human volunteers should be clearly formulated in an experimental protocol which should be transmitted for consideration, comment and guidance to a specially appointed committee independent of the Investigator and the Sponsor provided that this independent committee is in conformity with the laws and regulations of the country in which the research experiment is performed.

Biomedical research on human volunteers should be conducted only by scientifically qualified persons and under the supervision of a clinically competent medical person. The responsibility for the human volunteer must always rest with a medically qualified person and never rest on the volunteer of the research, even though the volunteer has given his or her consent.

Biomedical research involving human volunteers cannot legitimately be carried out unless the importance of the objective is in proportion to the inherent risk to the volunteer.

Every biomedical research project involving human volunteers should be preceded by careful assessment of predictable risks in comparison with foreseeable benefits to the volunteer or to others. Concern for the interest of the volunteer must always prevail over the interests of science and society.

The right of the research volunteer to safeguard his or her integrity must always be respected. Every precaution should be taken to respect the privacy of the volunteer and to minimise the impact of the study on the volunteer's physical and mental integrity and on the personality of the volunteer.

Physicians should abstain from engaging in research projects involving human volunteers unless they are satisfied that the hazards involved are believed to be predictable. Physicians should cease any investigation if the hazards are found to outweigh the potential benefits.

In publication of the results of his or her research, the physician is obliged to preserve the accuracy of the results. Reports on experimentation not in accordance with the principles laid down in this Declaration should not be accepted for publication.

In any research on human beings, each potential volunteer must be adequately informed of the aims, methods, anticipated benefits and potential hazards of the study and the discomfort it may entail. He or she should be informed that he or she is at liberty to abstain from participation in the study and that he or she is free to withdraw his or her consent to participation at any time. The physician should then obtain the volunteer's freely-given informed consent, preferably in writing.

When obtaining informed consent for the research project the physician should be particularly cautious if the volunteer is in a dependent relationship to him or her or may consent under duress. In that case the informed consent should be obtained by a physician who is not engaged in the investigation and who is completely independent of this official relationship.

In the case of legal incompetence, informed consent should be obtained from the legal guardian in accordance with national legislation. Where physical or mental incapacity makes it impossible to obtain informed consent, or when the volunteer is a minor, permission from the responsible relative replaces that of the volunteer in accordance with national legislation.

Whenever the minor child is in fact able to give consent, the minor's consent must be obtained in addition to the consent of the minor's legal guardian.

The research protocol should always contain a statement of the ethical considerations involved and should indicate that the principles enunciated in the present Declaration are complied with.

II. Medical Research Combined with Professional Care (CLINICAL RESEARCH)

In the treatment of the sick person, the physician must be free to use a new diagnostic and therapeutic measure, if in his or her judgement it offers hope of saving life, re-establishing health or alleviating suffering.

The potential benefits, hazards and discomfort of a new method should be weighed against the advantages of the best current diagnostic and therapeutic methods.

In any medical study, every patient - including those of a control group, if any - should be assured of the best proven diagnostic and therapeutic method. This does not exclude the use of inert placebo in studies where no proven diagnostic or therapeutic method exists.

The refusal of the patient to participate in a study must never interfere with the physician-patient relationship.

If the physician considers it essential not to obtain informed consent, the specific reasons for this proposal should be stated in the experimental protocol for transmission to the independent committee.

The physician can combine medical research with professional care, the objective being the acquisition of new medical knowledge, only to the extent that medical research is justified by its potential diagnostic or therapeutic value for the patient

[figure not shown]
III. Non-Therapeutic Biomedical Research Involving Human Volunteers
(NON-CLINICAL BIOMEDICAL RESEARCH)

[figure not shown]
In the purely scientific application of medical research carried out on a human being, it is the duty of the physician to remain the protector of the life and health of that person on whom biomedical research is being carried out.

[figure not shown]
The volunteer should be volunteers - either healthy persons or patients for whom the experimental design is not related to the patient's illness.

[figure not shown]
The Investigator or the investigating team should discontinue the research if in his/her or their judgement it may, if continued, be harmful to the individual.

[figure not shown]
In research on man, the interest of science and society should never take precedence over considerations related to the well-being of the volunteer.

[figure not shown]

[figure not shown]

[figure not shown]

[figure not shown]

[figure not shown]

[figure not shown]

[figure not shown]

[figure not shown]

[figure not shown]

[figure not shown]

[figure not shown]

26.6. Vitreous Haze Grading Scale

NUSSENBLATT CHART

## Statistical Analysis Plan

Sponsor:	Gyroscope Therapeutics		
Protocol:	GT005-01 (FOCUS)		
Document Version No.:	04.00	Document Date:	17-JUN-2024

## Statistical Analysis Plan

Sponsor:	Gyroscope Therapeutics		
Protocol:	GT005-01 (FOCUS)		
Document Version No.:	04.0	Document Date:	17-JUN-2024

## Statistical Analysis Plan

Sponsor:	Gyroscope Therapeutics		
Protocol:	GT005-01 (FOCUS)		
Document Version No.:	04.0	Document Date:	17-JUN-2024

## Statistical Analysis Plan

Sponsor:	Gyroscope Therapeutics		
Protocol:	GT005-01 (FOCUS)		
Document Version No.:	04.0	Document Date:	17-JUN-2024

## DOCUMENT HISTORY

Date	Time point	Reason for update	Outcome for update	Section and title impacted (Current)
06-FEB-2023	Prior to 1st LA DB lock	N/A	First version	NA
28-JUN-2023	Prior to 2nd LA DB lock	Sponsor Decision	
Clarified unscheduled visit handling
 
Removed post-baseline subgroup definitions for subgroup analysis, added correlation plot for GA area growth vs CFI level changes.
  	Section 3.1.1 Section 3.7
24-NOV-2023	Prior to final DB lock	Sponsor Decision	
Defined representation of data for study cohorts with different cutoff dates (Week 96 for TVSI, Week 48 for SDS Orbit)
 
Removed subgroup analysis, corrected order of MMRM covariance matrices to be used.
 
Added percentage of patients with full dose delivery for evaluation of successful delivery for Orbit SDS cohorts
  	Section 3.10 Section 3.7 Section 3.7

## Statistical Analysis Plan

Sponsor:	Gyroscope Therapeutics		
Protocol:	GT005-01 (FOCUS)		
Document Version No.:	04.0	Document Date:	17-JUN-2024

### ABBREVIATIONS

Abbreviation	Definition
ACC	Reading accessibility index
AE	Adverse events
AMD	Age-related macular degeneration
BCEA	Bivariate contour ellipse area
BCVA	Best corrected visual acuity
CFI	Complement Factor I
CNV	Choroidal neovascularization
CPS	Critical print size
CSR	Clinical study report
DSMB	Data Safety Monitoring Board
ETDRS	Early treatment for diabetic retinopathy
FAF	Fundus autofluorescence
FAS	Full Analysis Set
FIH	First in human
GA	Geographic atrophy (also known as macular atrophy)
hCFI	Human CFI
ICH	International Conference on Harmonisation
LLVA	Low luminance visual acuity
MedDRA	Medical Dictionary for Regulatory Activities
RV	Rare variant
SAE	Serious adverse event
SAP	Statistical analysis plan

## Statistical Analysis Plan

Sponsor:	Gyroscope Therapeutics		
Protocol:	GT005-01 (FOCUS)		
Document Version No.:	04.0	Document Date:	17-JUN-2024

Abbreviation	Definition
SD-OCT	Spectral domain optical coherence tomography
SDS	Subretinal Delivery System
[REDACTED]	[REDACTED]
SOC	System Organ Class
[REDACTED]	[REDACTED]
TEAE	Treatment emergent adverse event
TESAE	Treatment emergent serious adverse event
[REDACTED]	[REDACTED]
WHO	World Health Organization

## Statistical Analysis Plan

Sponsor:	Gyroscope Therapeutics		
Protocol:	GT005-01 (FOCUS)		
Document Version No.:	04.0	Document Date:	17-JUN-2024

### 1. INTRODUCTION

This Statistical Analysis Plan (SAP) describes the statistical methodology and data handling of the data collected in the clinical trial for Gyroscope Therapeutics with Protocol GT005-01: FOCUS: An open label first in human Phase I/II multicentre study to evaluate the safety, dose response and efficacy of GT005 administered as a single subretinal injection in subjects with Macular Atrophy due to Age-related Macular Degeneration (AMD). This SAP is based on the Clinical Study Protocol v 9.0, dated 15 December 2022.

The planned analyses identified in this SAP provide the basis for the results section of the clinical study reports and may be used in regulatory submissions or publications. Any differences in the planned analyses relative to the study protocol will be highlighted in the CSRs.

#### 1.1. Study design

This is an open label first in human (FIH) Phase I/II multicenter study to evaluate the safety, dose response and efficacy of GT005 in subjects with geographic atrophy (GA) due to AMD. The study will be conducted in four parts and approximately 65 subjects will be enrolled.

Part 1 (dose-escalation) will test three dose cohorts (██████████ vg), 3-5 subjects per cohort, with GT005 delivered via the transvitreal procedure.

[figure not shown]
Part 2 (dose-expansion) will enroll up to 20 subjects in Cohort 4 with GT005 delivered via the transvitreal procedure.

Part 3 (dose-escalation and evaluation of two doses of GT005 delivered with the Orbit Subretinal Delivery System (SDS); subretinal delivery via a suprachoroidal cannulation) will enroll 3-5 subjects at the mid and high dose (██████████ vg, Cohorts 5 and 6). Part 3 is independent of, and may be conducted in parallel to, Part 2.

Part 4 (dose-expansion) will enroll up to 20 subjects in Cohort 7 with GT005 delivered with the Orbit SDS.

The study will, for the individual subjects, consist of up to 14 visits over a 5-year period and will involve an independent Data Safety Monitoring Board (DSMB). For further details, refer to the GT005-01 Protocol.

**Figure 1** Overview of the study design

## Statistical Analysis Plan

[figure not shown]
Sponsor:	Gyroscope Therapeutics		
Protocol:	GT005-01 (FOCUS)		
Document Version No.:	04.0	Document Date:	17-JUN-2024

### 1.2. Study objectives and endpoints

Study objectives and related endpoints are described in Table 1 below.

[figure not shown]
**Table 1** Objectives and related endpoints

Objectives	Evaluation Criteria
Primary	
To evaluate the safety of GT005 at 3 doses	

Incidence of ocular and non-ocular treatment-emergent AEs (TEAEs) and treatment-emergent serious AEs (TESAEs) over 48 weeks

Secondary	
To evaluate the long-term safety of GT005 at 3 doses	

Incidence of ocular and non-ocular treatment-emergent AEs (TEAEs) and treatment-emergent serious AEs (TESAEs) up to 240 weeks

To evaluate the effect of GT005 on anatomical and functional visual outcomes	

Best corrected visual acuity (BCVA) and low luminance visual acuity (LLVA) score via the early treatment diabetic retinopathy study (ETDRS) chart up to 240 weeks

Macular sensitivity as assessed by Mesopic Micropertimetry up to 240 weeks

Change in GA area size as assessed by fundus autofluorescence (FAF) up to 240 weeks

To evaluate the performance of the Orbit SDS (US only)	

Rate of successful delivery of balanced salt solution (BSS) or BSS PLUS to the subretinal space

Rate of successful delivery of GT005 to the subretinal space

To evaluate the safety of the Orbit SDS (US only)	

Incidence of device-related AEs and SAEs

## Statistical Analysis Plan

Sponsor:	Gyroscope Therapeutics		
Protocol:	GT005-01 (FOCUS)		
Document Version No.:	04.0	Document Date:	17-JUN-2024

## Statistical Analysis Plan

Sponsor:	Gyroscope Therapeutics		
Protocol:	GT005-01 (FOCUS)		
Document Version No.:	04.0	Document Date:	17-JUN-2024

## 2. SUBJECT POPULATIONS

### 2.1. Population definitions

The **All Enrolled Set** includes all patients who signed informed consent. This analysis set will be used to summarize patient disposition and for summaries of successful GT005 and BSS delivery rates of SDS orbit device.

The **Safety Analysis Set (SAF)** will include all subjects who have undergone surgery and received GT005. The SAF will be used for analysis of safety and laboratory data.

The **Full Analysis Set (FAS)** will include all subjects in SAF who have baseline and at least one post baseline value of GA area size via FAF in the study eye. The FAS will be used for analysis of efficacy data.

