11.2. Population for Analysis

Two analysis sets will be defined. The Safety Analysis Set (SAF) will include all subjects who have undergone surgery and received GT005. The SAF will be used for analysis of safety and laboratory data. The Full Analysis Set (FAS) will include all subjects in SAF who have baseline and at least one post-baseline value of GA area size via FAF in the study eye. The FAS will be used for analysis of efficacy data.

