### 3.4. Subject disposition

The following summaries will be included in the disposition table considering all enrolled patients: number and percent of patients who are enrolled into the study, failed screening, treated, discontinued the study prior to or at the study week of the analysis (including reasons for discontinuation) by treatment dose, route of administration and overall.

A listing of patients who discontinue from the study prior to the end of study will be provided by treatment dose and route of administration. The listing will identify date, study day and the reason of study discontinuation.

Patients who sign an informed consent form and who are subsequently found to be ineligible prior to study treatment will be considered a screen failure. Screen failure information will not be summarized but only listed.

Number and percent of enrolled patients who were excluded (i.e., not evaluable) from SAF or FAS will be presented. A listing of patients and the reason of exclusion from corresponding analysis set will also be presented.

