### 3.5. Demographic and baseline characteristics

Demographics and baseline ocular characteristics for the study eye will be summarized with descriptive statistics for the FAS by dose, route of administration and overall. Demographic characteristics will include age, gender, race, ethnicity and CFI rare variant subgroup. Baseline ocular characteristics for the study eye will be additionally summarized by CFI variant subgroups per route of administration. Ocular baseline characteristics include:

- Study eye selection (left eye OS or right eye OD)
- Best corrected visual acuity BCVA (in ETDRS letters)
- Low-luminance visual acuity LLVA (in ETDRS letters)
- Low-luminance deficit (BCVA-LLVA, in ETDRS letters)
- GA lesion area (mm^2) as assessed by FAF
- GA contour (Unifocal, Multifocal) as assessed by FAF
- GA foveal involvement (Foveal, Extrafoveal) as assessed by FAF and OCT
- Junctional zone pattern (Atypical, Banded, Diffuse, Focal, Cannot Grade) as assessed by FAF
- Drusen area (mm^2) as assessed by CFP
- Presence of hard drusen (Yes, No, Cannot Grade) as assessed by CFP
- Maximum drusen size within ETDRS Grid (Large, Intermediate, Small, Cannot Grade) as assessed by CFP
- Presence of reticular pseudodrusen (Yes, No, Cannot Grade) as assessed by OCT
- Presence of soft drusen (Yes, No, Cannot Grade) as assessed by CFP
- Presence of calcified drusen (Yes, No) as assessed by CFP

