### 3.7. Efficacy analyses

Efficacy analyses will be conducted using the FAS by treatment dose and route of administration.

**GA area (mm^2)** change from baseline in the study eye as assessed by FAF will be presented in spaghetti plots and in a summary by visit table. It will also be summarized in a table and line plots as least-squares means with 95% CI by visit using MMRM model with fixed effects for treatment (defined as dose and route of administration), study visit, baseline GA area (mm^2), treatment by visit interaction and visit by baseline GA area interaction.

**Square root of GA area (mm)** change from baseline in the study eye will be presented in spaghetti plots and in a summary by visit table. It will also be summarized in a table and line plots as least-squares means with 95% CI by visit using MMRM model with fixed effects for treatment, study visit, square root of baseline GA area (mm), treatment by visit interaction and visit by square root of baseline GA area (mm) interaction. MMRM analysis will be repeated for CFI rare variant subgroups and [REDACTED] by replacing in the model treatment with subgroups of interest.

For MMRM analysis an unstructured covariance matrix will be used to model the within-patient error. If an MMRM model with an unstructured covariance matrix does not converge, a more restricted covariance matrix can be considered in the following order until convergence is reached: first-order autoregressive, Toeplitz, compound symmetry and variance components.

Additionally, scatter plots with linear trend lines for square root of GA area size (mm) change from baseline at the target analysis visit vs. last observed CFI levels before the target analysis visit in the vitreous and aqueous samples will be generated by treatment groups.

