## Statistical Analysis Plan

Sponsor:	Gyroscope Therapeutics		
Protocol:	GT005-01 (FOCUS)		
Document Version No.:	04.0	Document Date:	17-JUN-2024

The following **macular sensitivity parameters by Mesopic Microperimetry** will be summarized by visit:

- Fixation stability measured with bivariate contour ellipse area (BCEA) at 63% and 95% proportional values (Deg)
- Mean sensitivity (dB)
- Number of scotomatous points
- Percentage of fixation loss

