## Statistical Analysis Plan

Sponsor:	Gyroscope Therapeutics		
Protocol:	GT005-01 (FOCUS)		
Document Version No.:	04.0	Document Date:	17-JUN-2024

**The rate of successful delivery of full dose GT005** to the subretinal space for patients treated using the Orbit Subretinal Delivery System (cohorts 5-7) will be reported as number of full doses delivered divided by number of Orbit SDS devices used. **Rate of successful balanced salt solution (BSS/BSS+)** delivered will be reported as number of BSS/BSS+ administrations divided by number of devices used. Additionally, percentage of patients with full dose of GT005 delivered among patients intended to be treated using SDS Orbit will be reported. Listing of failed deliveries of GT005 or balanced salt solution (BSS/BSS+) will be provided along with the reasons for delivery failures.

All efficacy endpoints will be provided in data listings for FAS.

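### The baseline table uses the FAS, which requires a post-dose FAF value, while the primary safety endpoint is reported on the SAF

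*SAP*

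**What the plan says.** SAP 2.1 defines the SAF as all subjects who had surgery and received GT005, and the FAS as "all subjects in SAF who have baseline and at least one post baseline value of GA area size via FAF in the study eye". Protocol 11.2 defines both sets the same way.

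Each set has a stated purpose. For the SAF, SAP 2.1 says: "The SAF will be used for analysis of safety and laboratory data". For the FAS, Protocol 11.2 says: "The FAS will be used for analysis of efficacy data". Neither statement mentions baseline data, and Protocol 11.3.1, which describes the baseline summaries, names no analysis set.

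SAP 3.5 makes the choice: "Demographics and baseline ocular characteristics for the study eye will be summarized with descriptive statistics for the FAS". SAP 3.7 says: "Efficacy analyses will be conducted using the FAS by treatment dose and route of administration". That section covers GA area and also the "macular sensitivity parameters by Mesopic Microperimetry", and it closes with: "All efficacy endpoints will be provided in data listings for FAS".

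The primary endpoint is the incidence of treatment-emergent adverse events and serious adverse events over 48 weeks (SAP 1.2). SAP 3.9.1 analyses adverse events on the SAF.

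On disclosure, SAP 3.4 says: "Number and percent of enrolled patients who were excluded (i.e., not evaluable) from SAF or FAS will be presented". A listing with the reason for each exclusion is also planned.

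**The concern.** A baseline table should describe the people behind the main result. Here the main result is safety in every dosed subject, but the baseline table is limited to dosed subjects who later yielded a measurable lesion area on FAF. Whether someone appears in a table of pre-treatment characteristics thus depends on something that happens after treatment.

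For GA area the condition does no harm, because a subject with no post-dose FAF has no change to analyse. Age, sex, baseline lesion size and baseline acuity need no post-dose image. A subject who was dosed, had adverse events and left before any FAF would be in the numerator and denominator of the safety tables, and the reader would not see that subject in the description of the treated population.

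This also sits awkwardly with Protocol 11.3, which asks that data from subjects who withdraw early be included in presentations wherever possible. Including their baseline data is plainly possible. Within the SAP itself, medical history (3.6) and reportable protocol deviations (2.2) are already on the SAF, so the baseline table is out of line with comparable outputs.

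**Working it through.** **The plan's own figure.** The only sample figure is planned enrolment, the sum of the cohort maxima in Protocol 3.1: 3 × 5 + 20 + 2 × 5 + 20 = 65, which agrees with the stated figure of approximately 65. There is no power calculation or assumed dropout rate to reproduce (SAP 3.3).

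**Which output uses which set.**

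| Output | Set | Source | Needs a post-dose FAF? |
|---|---|---|---|
| Adverse events (primary) | SAF | SAP 3.9.1 | No |
| Medical history | SAF | SAP 3.6 | No |
| Reportable protocol deviations | SAF | SAP 2.2 | No |
| Demographics and baseline characteristics | FAS | SAP 3.5 | No |
| GA area | FAS | SAP 3.7 | Yes |
| Microperimetry | FAS | SAP 3.7 | No |
| BCVA, LLVA, low-luminance deficit | None named; placed under Safety Analyses | SAP 3.9.2 | No |

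**Which half of the FAS condition matters.** Lesion size must be established for eligibility, and the central reader assesses the lesion before enrolment (Protocol 4.2 and 7.1). The baseline requirement should therefore rarely exclude anyone. The post-baseline requirement is the one that can.

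**When FAF and microperimetry are done** (Protocol Tables 2 and 3, and sections 7.6 to 7.18):

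- Post-dose FAF: Weeks 5, 12, 24, 36 and 48, the long-term visits, and early termination.
- Post-dose microperimetry: Weeks 12, 24 and 48, the long-term visits, and early termination, at sites with the device.

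FAF is scheduled at every visit that has microperimetry. Three cases follow.

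1. A subject leaves before Week 5 with no early termination FAF. There are baseline and adverse-event data but no scheduled post-dose microperimetry. The subject is missing from the baseline table, and no microperimetry result is lost.
2. A subject leaves early but attends an early termination visit with a measurable FAF. The subject is in the FAS and nothing is lost.
3. A subject stays and performs microperimetry but has no measurable FAF at any post-dose visit. The subject is missing from the baseline table, the microperimetry summaries and the FAS efficacy listings.

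**Size of one exclusion.**

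- 1/3 = 33% of a cell of 3
- 1/5 = 20% of a cell of 5
- 1/20 = 5% of a cohort of 20
- 1/65 = 1.5% of the whole study

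**How often.** The documents give no rate of missing post-dose FAF. Suppose a fraction *q* of dosed subjects has none, independently. The expected number lost of 65 is 65*q*, and the chance that a group of 5 loses at least one is 1 − (1 − *q*)^5.

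| Assumed *q* | Expected loss of 65 | Chance a group of 5 loses at least one |
|---|---|---|
| 2% | 1.3 | 1 − 0.98^5 = 10% |
| 5% | 3.25 | 1 − 0.95^5 = 23% |
| 10% | 6.5 | 1 − 0.90^5 = 41% |

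These rates are assumptions chosen to show a range. They are not estimates from the documents.

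**The case against.** The best case for leaving the plan alone has several parts.

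*The exclusions are disclosed.* SAP 3.4 gives the count, the percentage and a listing with reasons, and SAP 3.2 promises that all recorded data will appear in listings. This stands: excluded subjects do not disappear from the report, and they stay in disposition and in the safety tables. But the percentage is of everyone enrolled, which SAP 2.1 defines by signed consent rather than dosing, and a listing does not give the reader a baseline summary of the safety population.

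*The FAS matches the protocol.* It does, as a set for efficacy. Its use for baseline data is the SAP's own choice.

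*The affected share is usually smaller than 20 to 33%.* Summaries are by dose and route, and Cohorts 4 and 7 can add up to 20 subjects each. The larger percentages apply only to cells without expansion subjects. This stands.

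*Microperimetry is hardly touched.* This largely stands. A reader might infer that early leavers lose microperimetry results because of the FAF rule. The schedule does not support that: only the third case above is affected.

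*Visual acuity is not affected.* A reader might also infer that eyes with a poor surgical course drop out of the BCVA and LLVA summaries, since acuity is listed among the functional outcomes. The documents do not support this. SAP 3.9.2 belongs to Safety Analyses, SAP 2.1 assigns safety data to the SAF, and all acuity assessments are to be listed without a FAS limit.

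**Conclusion.** The point holds for the baseline table. A dosed subject with no post-dose FAF would be in the primary safety tables and missing from the description of the population, and no planned table fills the gap. The microperimetry part holds only for a subject who performs that test but never has a measurable post-dose FAF, which should be rare.

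The size is at most modest: one subject is 20 to 33% of a cell of 3 to 5 and about 5% of a 20-subject cohort. How often this happens is unknown, and if every dosed subject has a post-dose FAF the two sets coincide. The study tests no hypotheses, so no formal inference depends on it.

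It would be tempting to conclude that the functional results are biased in a favourable direction. The documents give no data on who would lack FAF or how such eyes would fare, so that conclusion is not supported. This is an inexpensive improvement to reporting and does not challenge the primary analysis.

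**What to change.** **Main change, SAP 3.5.** Summarise demographics and baseline ocular characteristics on the SAF. If the SAF and FAS differ, add the FAS version as a supplement, so that the GA area results also have a matching baseline description. Because Protocol 11.3.1 names no set for baseline data, this does not depart from the protocol.

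**Secondary change, SAP 3.7.** Summarise and list microperimetry for SAF subjects with a baseline and at least one post-baseline microperimetry value. Protocol 11.2 puts efficacy data on the FAS and Protocol 11.3.2 counts microperimetry as efficacy, so record this in SAP section 4, which at present declares no changes. If the sponsor prefers to stay with the protocol here, little is lost.

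**Cost.** No new data are needed. The main change is a wording edit plus, at most, one extra table; the secondary one also needs the entry in section 4. The downside is that subject numbers may differ slightly between the GA area tables and the others, which a footnote can explain.
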